### **10.3. Data Retention**

Record retention period will be determined by country and/or site-specific requirements. At a minimum, records must be retained for at least 2 years beyond the date of PMA supplement approval or 2 years beyond the termination of this study, in the case of the Sponsor's decision not to pursue a PMA supplement.

### **10.4. Confidentiality**

The investigators and Sponsor (and its parent company, Teleflex Incorporated) commit to maintaining the confidentiality of individual data of subjects involved in the study. All data collection forms and related documents will be submitted using unique, confidential subject identification numbers. All documents submitted to the Sponsor will be maintained in strict confidence.

Each subject's data will be completely de-identified in the final reports and subsequent publications in order to maintain subject confidentiality. All investigators and study site staff must comply with the requirements of all applicable U.S. (e.g., HIPAA) or Canadian laws and local regulations with regards to the collection, storage, processing and disclosure of personally identifying medical information.

### **10.5. Protocol Deviations**

A protocol deviation is defined as any instance during the conduct of the study in which the investigator or other site personnel changed or failed to adhere to the study design or procedures specified by this protocol. Examples of protocol deviations may include (but are not limited to):

- Enrollment of a study subject who does not meet all of the inclusion/exclusion criteria specified in this protocol;
- Failure to obtain a specified data element or endpoint (e.g., lab test results, TTH, safety events, etc.); or
- Enrollment of a patient during a lapse in IRB/REB approval of the study.

All relevant protocol deviations should be submitted by the site on the applicable eCRF, and will be reviewed and assessed for their impact on subject safety and data analysis by the sponsor or its designee. Investigational sites are expected to comply with this study protocol except where necessary to protect the life or physical well-being of a subject in an emergency (in cases of medical emergency, the Sponsor should be notified within 24 hours of the occurrence of the event).

Investigational sites should report deviations to their IRBs/REBs per their local requirements.

### **10.6. Investigator Disqualification Criteria**

The Sponsor reserves the right to terminate an investigator/observational site for any of the following reasons:

- Failure to secure subject informed consent, including protection of personal data, prior to enrollment.
- Failure to report serious adverse device effects within 24 hours of discovery.
- Repeated observational plan deviations.

- Repeated failure to appropriately complete eCRFs.
- Failure to enroll an adequate number of subjects.
- Loss of or unaccounted for investigational product inventory.

## 11. Adverse Events

### 11.1. Definitions

All of the following adverse event terms are defined in Appendix A-Definitions:

- Adverse Event (AE)
- Adverse Device Effect (ADE)
- Device Deficiency (DD)
- Serious Adverse Event (SAE)
- Serious Adverse Device Effect (SADE)
- Unanticipated (Serious) Adverse Device Effect (UADE/USADE)

### 11.2. Potential Adverse Events and Adverse Device Effects

The following potential adverse events are related to the deployment of VCDs:

- Ischemia of the leg or stenosis of the femoral artery
- Local trauma to the femoral or iliac artery wall, such as dissection
- Retroperitoneal bleeding, and its consequences, as a result of failed closure in the setting of an access above the inguinal ligament or the most inferior border of the epigastric artery
- Perforation of iliofemoral arteries, causing bleeding or hemorrhage
- Thrombosis formation or embolism
- Adjacent nerve damage or neuropathy
- Other access site complications leading to bleeding, hematoma, pseudoaneurysm, or arterio-venous fistula, possibly requiring blood transfusion and/or surgical intervention

Potential Adverse Events and Adverse Device Effects associated with any large bore intervention, including the use of the MANTA VCD, include but are not limited to:

- Arterial damage
- Arterio-venous fistula
- Bradycardia
- Compartment Syndrome
- Death related to procedure
- Deep vein thrombosis
- Ecchymosis
- Edema
- Infection at the puncture site which may require antibiotics or extended hospitalization
- Inflammatory response
- Late arterial bleeding
- Oozing from the puncture site
- Pressure in groin/access site region

- Vessel laceration or trauma
- Wound dehiscence

### **11.3. Adverse Event (AE) Assessment**

Starting at the time an attempt is first made to use the MANTA VCD (including U/S use post TAVR valve deployment and prior to MANTA VCD use) and at each subsequent evaluation, the investigator will determine if any AEs have occurred in any subject. Subjects are encouraged to report AEs freely or in response to general, non-directed questioning. The subject may volunteer information that appears to be an AE anytime during the study. If an AE is determined to have occurred, the investigator should obtain all the required information and document findings on the eCRF.

In general, a primary diagnosis for the event should be reported instead of each symptom. Only exacerbated conditions or new onset qualify as an AE, but if patient history is in question, report AE conservatively.

### **11.4. Relatedness to Device or Procedure**

Each reported AE will be assessed by the Investigator for its primary suspected relationship to the U/S-guided MANTA VCD deployment/device or to the interventional procedure.

- Study AEs related to the interventional procedure (e.g., TAVR procedure) or closure of a non-target access site are considered Procedure-Related AEs.
- Study AEs related to the MANTA VCD and/or the U/S deployment method (in total, the closure procedure) are considered Device-Related AEs.
- Study AEs that are related to neither the interventional procedure nor use of the MANTA VCD are considered NOT related to the device or procedure.

The causal relationship of an AE to the device or procedure will be classified as follows:

**Not related**: relationship of the event to the device or procedure can be excluded when:

- the event is not a known side effect of the product category the device belongs to or of similar devices and procedures;
- the event has no temporal relationship with the use of the investigational device or the procedures;
- the event does not follow a known response pattern to the medical device (if the response pattern is previously known) and is biologically implausible;
- the discontinuation of medical device application or the reduction of the level of activation/exposure – when clinically feasible – and reintroduction of its use (or increase of the level of activation/exposure), do not impact on the event;
- the event involves a body-site or an organ not expected to be affected by the device or procedure
- the event can be attributed to another cause (e.g. an underlying or concurrent illness/ clinical condition, an effect of another device, drug, treatment or other risk factors);
- harms to the subject are not clearly due to use error;

In order to establish the non-relatedness, not all the criteria listed above might be met at the same time, depending on the type of device/procedures and the adverse event.

**Possible:** relationship of the event with use of the investigational device or the procedure is weak but cannot be ruled out completely. Alternative causes are also possible (e.g., an underlying or concurrent illness/ clinical condition or/and an effect of another device, drug or treatment). Cases where relatedness cannot be assessed or no information has been obtained should also be classified as possible.

**Probable:** relationship of the event with use of the investigational device or the procedure seems relevant and/or the event cannot reasonably be explained by another cause, but additional information may be obtained.

**Causal relationship:** the event is associated with the investigational device or procedure beyond a reasonable doubt when:

- the event is a known side effect of the product category the device belongs to or of similar devices and procedures;
- the event has a temporal relationship with investigational device use/application or procedures;
- the event involves a body-site or organ that:
  - the investigational device or procedure is applied to
  - The investigational device or procedure have an effect on;
- the event follows a known response pattern to the medical device (if the response pattern is previously known);
- the discontinuation of medical device application (or reduction of the level of activation/exposure) and reintroduction of its use (or increase of the level of activation/exposure), impact on the event (when clinically feasible);
- other possible causes (e.g., an underlying or concurrent illness/ clinical condition or/and an effect of another device, drug or treatment) have been adequately ruled out;
- harm to the subject is due to error in use.

In order to establish the relatedness, not all criteria listed above might be met at the same time depending on the type of device/procedures and the serious event.

### 11.5. Severity of Adverse Events

The following categories will be used to describe the severity of an AE:

- Mild: awareness of a sign or symptom that does not interfere with the subject's usual activity or is transient, resolved without treatment and with no sequelae.
- Moderate: interferes with the subject's usual activity and/or requires symptomatic treatment.
- Severe: symptom(s) causing severe discomfort and significant impact on the subject's usual activity and requires treatment.

### 11.6. AE and Serious Adverse Event (SAE) Reporting to Sponsor

All SAEs, irrespective of potential causal relationship to the device, procedure or study, that occur from the point of attempted MANTA VCD placement (including U/S use post TAVR completion and prior to MANTA VCD use) onwards will be reported to the Sponsor within 24

hours of the Investigator's first knowledge of the event. Suspected SAEs also should be reported.

The Investigator will forward information, via the eCRF system, about an SAE promptly, even if the information is incomplete or it is obvious that more data will be needed to form any conclusions. This information will be available to the Sponsor and CRO in the database. Additional information regarding the SAE will be recorded on the follow-up AE form forwarded to the Sponsor.

All AEs should be reported on the eCRF as soon as practicably possible. AEs will be recorded by their final medical diagnosis and not by each separate symptom. The information for the event will include the date of awareness, onset and resolution, the action taken, the corrective treatment and how the subject recovered with or without sequelae. In case of death, the relationship of death to the investigational device and/or the study procedure will be well documented. The date on which subject expired, what attempts were made to treat the event that led to death, the performance and functioning of the device during the event will be noted.

## **11.7. IRB and Regulatory Agency Reporting of Adverse Events**

### **11.7.1. U.S. Sites**

The Investigator is responsible for reporting SAEs, in the required timeframe, to his/her IRB as required by the IRB.

The Sponsor is responsible for reporting UADEs to the U.S FDA in accordance with the IDE regulations (21 CFR Part 812). The results of any evaluation that has determined a UADE has occurred will be reported to FDA and all reviewing IRBs and participating investigators within 10 working days after receiving notice of the UADE, per 812.150(b)(1).

The Sponsor will notify device-related SAE information to all active study Investigators as it becomes available.

### **11.7.2. Canadian Sites**

The Investigator is responsible for reporting SAEs, in the required timeframe, to his/her REB as required by the REB. The investigator is also responsible for notifying Health Canada of any events that meet the definition of an "incident" under the Canadian Medical Device Problem Reporting requirements.

The Sponsor is responsible for reporting device-related incidents to Health Canada in accordance with the Canadian Medical Device Problem Reporting requirements.

### **11.7.3. Device Deficiencies**

The Investigator will record any device deficiencies, as defined in Appendix A, in the eCRF. A device deficiency has occurred if an investigational device used in the study procedure failed to meet its performance specifications whether due to mechanical failure, malfunction or defects. Device deficiencies also include use errors and inadequate labeling. This applies to:

- devices used in the subject; or
- devices in which the package was opened, but the device was not used on the subject; or

- devices with which at least one insertion attempt was made, but the device did not remain in the subject.

If the device deficiency was associated with an AE, the reporting provisions for AE, ADE, SAE, SADE, UADE and USADE as outlined above apply. Any device deficiency that did not lead to an AE but could have led to a SADE, if suitable action had not been taken, if intervention had not been made, or if circumstances had been less fortunate, must be reported to the Sponsor within 24 hours of the event using the eCRF. Reporting will follow the guidelines above. All device deficiencies will be recorded on the eCRF. Device deficiencies which could not have led to a SADE must be reported to the Sponsor within 3 business days. All devices alleged to be deficient must be returned to the Sponsor within 5 business days.

## 12. Clinical Events Committee

An independent Clinical Events Committee (CEC) will be established for this study. The CEC will consist of three interventional cardiologist physicians. CEC members will be chosen based on their clinical expertise and have no association with this study for which they will adjudicate events. Prior to the start of subject enrollment, the CEC will approve a charter containing criteria for event evaluation.

The CEC will be responsible for adjudicating the following events and determining their device and procedure relatedness:

- All Adverse Events that are categorized by the investigator on the eCRF as “associated with the target artery and/or the ipsilateral leg (not the contralateral side)”;
- All Adverse Events marked on the eCRF that are categorized by the investigator as having a possible, probable or causal relationship with the MANTA device.

The CEC will classify each AE as to whether it is a LBAR VARC-2 Major or LBAR VARC-2 Minor complication or neither. Analysis of the primary and secondary safety endpoints will be based on CEC adjudicated data.

In some cases, grouping of inter-related adverse events into a primary adverse event may be appropriate due to all events being symptoms of the same incident. The CEC will select the primary event among the inter-related site reported events.

Lastly, the CEC will also classify each AE whether it is a VARC-3 Major or VARC-3 Minor complication or neither.

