## 10.2. Data Management

The Sponsor or its designee will review the data against the original source documents and ensure any noted discrepancies are resolved by the investigational site, in accordance with the separate data management and monitoring plan(s). Subject data will be compared to information originally recorded on source documents related to the trial (e.g., professional notes, laboratory reports, investigation-specific worksheets, etc.). The extent of source document verification may be risk-based.

All information collected in the eCRFs will be entered directly into a secure database. The database design and installation will be validated prior to use.

The details of data review, database cleaning and data querying are described in a Data Management Plan (DMP). This plan may be updated throughout the investigation as amended data management requirements and investigation-specific data conventions are determined.

Data entered by investigational sites will be reviewed on an ongoing basis to ensure adequate query resolution and identify and query adverse events, protocol deviations, and any other ambiguous data points.

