6.7 Adverse Events and Device Deficiencies

Adverse events (AEs) and device deficiencies will be collected throughout this trial. AEs will be classified using the MedDRA coding system and will be summarized by System Organ Class and Preferred Term.

Adverse events that are determined to be related to the device or procedure (“associated with the target artery and/or the ipsilateral leg (not the contralateral side”) will be sent to the CEC for adjudication. The exact process will be finalized in the CEC charter. The CEC will adjudicate procedure and device relatedness of these events and whether events met an LBAR Major or Minor Complication. These adjudications will overrule investigator classifications for summarizing data.

For relatedness, classifications of Causal/Definite, Probably, Possible and Unknown (if any) will be considered related.

AEs will be summarized by count and proportion of subjects experiencing one or more events by seriousness, severity, device and procedure relatedness, and time period (day 0 (procedure)-discharge, discharge-30 days, 0-30 days, 31-60, 61-180 days, and 181-study exit).

Any UADEs, ADEs or SADEs will be summarized as well.

Device deficiencies collected on a separate eCRF form will also be summarized and indicate if any deficiencies resulted in any adverse events.

7 Poolability of Data

Analyses of the primary safety endpoint will be performed to assess the comparability of study sites. Sites with fewer than 5 subjects each will be included in summaries by site but excluded from poolability analysis.

LBAR Major Complications will be analyzed by Fisher's Exact test to assess if the Major Complication rates differ among study sites. If the study site rates differ ($p<0.15$) then additional analyses will be performed to explore the cause of the difference, in particular if the differences are caused by differences in some baseline factor.

8 Data Conventions and Missing Data

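### Referral to the CEC depends on how the investigator codes an event, so an access-related death or major bleed attributed to the TAVR procedure or another site has no clear route to adjudication; SAP 3, 6.3 and 6.7 disagree on the rule.

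*Protocol*

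**What the plan says.** **Referral rule.** Protocol 12 lists two groups of events for the CEC. The first is "All Adverse Events that are categorized by the investigator on the eCRF as" associated with the target artery or the ipsilateral leg. The second is events "categorized by the investigator as having a possible, probable or causal relationship with the MANTA device". SAP 3 repeats both. Relation to the TAVR procedure is not a trigger in either place.

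**Use of the result.** Protocol 12 states: "Analysis of the primary and secondary safety endpoints will be based on CEC adjudicated data". Protocol 15.3.2 applies this to the primary endpoint.

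**Endpoint scope.** Protocol 6.1 counts any access-site or access-related vascular injury that leads to death or to life-threatening or major bleeding, among other outcomes. Under Protocol Appendix A, transfusion of 2 or 3 units can make a bleed major, and 4 or more units life-threatening.

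**Other SAP wording.** SAP 6.3 says that the CEC will review AEs against the endpoint criteria and sets no limit by coding. SAP 6.7 sends "Adverse events that are determined to be related to the device or procedure" to the CEC, with the target-artery/leg phrase in brackets. It has no separate MANTA trigger and does not say who makes the determination. It adds: "The exact process will be finalized in the CEC charter".

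**Coding rules.** Under Protocol 11.4 a device relation is 'possible' when it is "weak but cannot be ruled out completely". The section also says: "Cases where relatedness cannot be assessed or no information has been obtained should also be classified as possible".

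**The concern.** The endpoint is defined by access-related injury. Referral is defined by where the investigator places the event and whether the investigator suspects MANTA, and these do not cover quite the same ground. Protocol 11.4 asks for the primary suspected relationship, either to the MANTA deployment or to the interventional procedure. An iliac injury from large-bore access, or a retroperitoneal bleed, could reasonably be coded to the TAVR procedure and not to the target femoral artery or the leg. It would then meet neither trigger, although the CEC might have judged it access-related.

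The investigator doing the coding knows which closure technique was used. The CEC can overrule coding on events it receives, but not on events it never sees. In a single-arm comparison with a fixed performance goal, a missed endpoint event can only lower the observed rate, and there is no control arm in which similar losses would offset it.

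Separately, the documents give three descriptions of what the CEC reviews: Protocol 12 with SAP 3, SAP 6.3, and SAP 6.7. Staff applying them could refer different events.

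**Working it through.** **1. The referral texts side by side**

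| Place | What goes to the CEC | Procedure-related bleed not coded to the target artery/leg or to MANTA |
|---|---|---|
| Protocol 12, SAP 3 | Target artery/leg, or possible, probable or causal relation to MANTA | Not listed |
| SAP 6.3 | AEs, unrestricted | Covered in words, but no mechanism is given |
| SAP 6.7 | Related to device or procedure, with the location phrase in brackets | Unclear: the leading words include it, the bracket appears to exclude it |
| CEC charter | Not available | Unknown |

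The accurate statement is that no clear referral rule exists in the protocol and SAP.

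**2. The plan's own sample size**

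Inputs: performance goal 14.2%, expected rate 4.2%, one-sided alpha 0.025, power at least 80%, stated n = 69 (Protocol 15.1 and 15.2); exact binomial test (SAP 6.3).

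Let c be the largest count with P(X ≤ c | n, 0.142) ≤ 0.025. Power is P(X ≤ c | n, 0.042).

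- n = 69: c = 4, attained alpha 0.0248, power 83.6%. The stated 69 is reproduced.
- n = 75, the analysed number: c is still 4.

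**3. The pass/fail boundary at N = 75**

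Exact (Clopper-Pearson) upper 97.5% bound = the 0.975 quantile of Beta(x + 1, 75 − x).

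| Subjects with an event | Upper bound | One-sided p against 14.2% | Result |
|---|---|---|---|
| 4 | 13.10% | 0.0134 | Pass |
| 5 | 14.88% | 0.0354 | Fail |

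A single unreferred endpoint event changes the result only when the true count is exactly 5. P(X = 5 | 75, p) is 11.2% at p = 4.2% and 2.2% at p = 14.2%.

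**4. Illustration with assumed losses**

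The documents give no loss fraction, so every f below is an assumption. If a fraction f of subjects with an endpoint event never reaches adjudication, independently of one another, the chance of passing is P(X ≤ 4 | 75, p(1 − f)). At a true rate of 14.2%:

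| Assumed loss f | Chance of a false pass |
|---|---|
| 0 | 1.3% |
| 5% | 2.0% |
| 10% | 3.0% |
| 20% | 6.2% |

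The nominal 2.5% is reached at f of about 7.8%. With 75 × 0.142 = 10.65 expected events, that is 0.078 × 10.65 ≈ 0.83 of an event.

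**The case against.** The case for leaving the text alone has real weight.

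- **The first trigger covers most of the endpoint.** Target-artery and ipsilateral-leg events are referred whatever their cause or severity. New ipsilateral ischemia and nerve injury, which Appendix A defines as ipsilateral, fall largely within it.
- **The second trigger is set low.** A weak or unassessable relation to the device counts as 'possible' and is referred. Protocol 11.2 also lists retroperitoneal bleeding from failed closure as a closure-device event.
- **Outcomes travel with their cause.** Protocol 11.3 and 11.6 ask for the diagnosis rather than each symptom, and the CEC groups inter-related events. A death or transfusion that follows a groin hematoma should reach the CEC through the hematoma.
- **Other safeguards exist.** Post-closure angiography and repeated access-site assessments are scheduled. All SAEs go to the sponsor within 24 hours whatever their cause (Protocol 11.6). Data review is meant to "identify and query adverse events, protocol deviations, and any other ambiguous data points" (Protocol 10.2). Source review looks for unreported AEs (Protocol 16.5), and two CEC physicians also sit on the DSMC (Protocol 13).
- **SAP 6.3 is unrestricted, and the charter may settle the matter.**

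All of this stands as a limit on size. It does not close the gap. None of these safeguards is a rule that sends an event already reported, but coded elsewhere, to the CEC. SAP 6.3 names no mechanism, and it conflicts with the explicit two-group list in SAP 3.

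A reader might infer that deaths and transfusions in general bypass adjudication. The documents do not support that: most access-related ones would arrive under an existing trigger. A reader might also take operator attributions in the earlier pivotal study (Protocol 3.3), such as the bleed ascribed to an inferior epigastric artery, as evidence of miscoding. They show only that such attributions are made.

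**Conclusion.** The point holds in a limited form. The protocol and SAP have no clear, consistent rule for referring an access-related death or major or life-threatening bleed that the investigator attributes to the TAVR procedure or another site. Such an event could be a primary endpoint event.

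The gap is narrow and of unknown, probably small, size. Its direction is known: it can only lower the observed rate. The margin is one event, since 4 of 75 passes and 5 of 75 fails.

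It would be tempting to conclude that the type I error exceeds 2.5%. The documents do not support this. With full capture it is 1.3% at N = 75, and it exceeds 2.5% only if more than about 7.8% of endpoint events are lost, a fraction for which there is no evidence either way.

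The conclusion rests on the protocol and SAP alone. If the charter already contains coding-independent triggers, what remains is to align the texts.

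**What to change.** Use one trigger list, worded identically, in Protocol 12, SAP 3, SAP 6.7 and the CEC charter, and have SAP 6.3 refer to it.

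- Keep the two existing triggers.
- Add, through 30 days and regardless of the investigator's location or relatedness coding:
  - all deaths;
  - all VARC-2 major or life-threatening bleeds, including those that meet Appendix A's transfusion criterion of 2 or more units;
  - all unplanned vascular interventions.
- State that the CEC then decides whether each event is related to the large-bore access site.

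Separate ischemia and nerve triggers are optional, because the first existing trigger largely covers them. If the charter already holds these triggers, copy them into the protocol and SAP.

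The cost is a wording change in the protocol, SAP and charter, and a modest number of extra cases for the existing three-member CEC. Many of these will be adjudicated as neither Major nor Minor, and the observed rate may rise slightly. The new triggers still depend on sites reporting the events, so the source review in Protocol 16.5 remains necessary. The endpoint definition, sample size and test stay as they are.
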